9.0 STUDY CALENDAR

	Screening	Prior to each dose	Monthly (CxD1)	Every 3 Month beginning C4,D1	End of Study Treatment Visit ⁵
PHYSICAL⁹					
History & Physical Exam, including liver assessment	X		X ⁷	X	X
Height	X				
ECOG Performance Status (see 10.4)	X	X		X	X
Vital Signs & Weight		X		X	
Adverse Event Monitoring		X		X	X
SF-36 (QOL)	X			X	
LABORATORY-Serum					
Complete Blood Count with Differential	X	X		X	X
Beta-HCG ¹	X				
Chemistry including: BUN, creatinine, glucose, sodium, potassium, chloride, bicarb, cholesterol, CK, calcium, total protein, LDH, magnesium, phosphorous, triglycerides, uric acid, TSH, amylase	X	X		X	X
BUN / Serum Creatinine	X	X		X	X
Creatinine Clearance ³	X				
Hepatic Function Testing: ALT/AST, Bilirubin, Albumin, Alkaline Phosphatase	X	X		X	X
β-2 Microglobulin / C-reactive protein	X			X	X
Cardiac enzymes: BNP/ Troponin I/NT ProBNP	X	X		X	X
Serum free light chain assay	X	X ⁸		X	X
SPEP, SIFE, Immunoglobulins	X			X	X
Coombs test; IAT (anti globulin test)	X				
Coagulation profile: PTT, INR, D-dimer, Factor X	X			X	X
HBV serology testing ¹⁰	X				
HBV DNA testing ¹¹	X				X
Type And Screen and blood bank phenotype ⁶	X				
Daratumumab-specific Immunofixation (patients with Kappa disease only)	X			X	X
LABORATORY-Urine					
Urinalysis	X			X	X
24 hour urine: total protein, creatinine, kappa, and lambda	X			X	X
UPEP / UIFE / TV	X			X	X
PATHOLOGY					
BM biopsy	X ²				
Fat aspirate (if not previously done)	X				
X-RAYS AND SCANS					
ECG / CXR	X				
Echocardiogram	X			Every 6 months	
PFTs (required for chronic smokers or known COPD)	X				

1 For women of childbearing potential only.

2 Bone marrow biopsy and aspiration must have been repeated following any previous therapy > 1 cycle.

3 CreatClear = Sex * ((140 - Age) / (SerumCreat)) * (Weight / 72); Equation parameters such as Sex have two or more discrete values that may be used in the calculation. The numbers in the parentheses, e.g. (1), represent the values that will be used. The default unit of measure for weight is kilograms. Please verify that the correct unit of measure has been selected. <http://reference.medscape.com/calculator/creatinine-clearance-cockcroft-gault>

4 While on study drug or until disease progression or start of another therapy.

5 30 days following last dose (+/-) 7 days.

6 Order type and screen and blood bank phenotype on patients prior to starting daratumumab and document in the order that the patient will be receiving daratumumab as notification to Blood Bank due to its interference with serological testing. See Section 7.3.
7 Full history and physical exam with liver measurements required monthly while on protocol. Limited physical examination at other visits only if clinically indicated.

8 If FLCs have normalized, full HAM1-5 panels to be completed at next visit.

9 Screening tests should be performed within 28 days of initiating study drug with the exception of Echocardiogram, CXR, PFTs and EKG, which could occur within 60 days.

10 HBV serology testing: HBsAg, antibody to antiHBs, and antibody to antiHBc assessments should be obtained for those on study treatment for less than 6 months at the time of amendment 11. Subjects who have serologic evidence of HBV exposure, but are HBsAg negative and do not have active HBV infection will have testing monitored every 3 months while on study treatment.

11. HBV DNA testing: Q12W during treatment, at the End of treatment visit, and Q12W for up to 6 months after last dose of study treatment. For subjects with serologic evidence of resolved HBV infection (i.e., positive Anti-HBs or positive Anti-HBc) at Screening, HBV DNA testing by PCR must be performed locally. See section 7.3

10.0 CRITERIA FOR EVALUATION AND ENDPOINT DEFINITIONS

Patients will not be required to have a delta FLC of 40 mg/L for study entry as primary endpoint of the study is to evaluate safety and tolerability of the study drug. Hematologic responses will be assessed by other hematologic measures of disease including M-spike and presence of clonal plasma cells in the bone marrow. Organ responses will be assessed by changes in 24 hour protein excretion for patients with renal involvement; by changes in NT-proBNP for patients with cardiac involvement; and by changes in alkaline phosphatase levels and liver span for patients with hepatic involvement.

10.1 Toxicities:

Safety of the study drug will be assessed by using vital sign information in addition to data pertaining to the duration of therapy, interruption of therapy, routine laboratory assessments, and frequency and severity of AEs

10.2 Responses:

It is important to note that daratumumab is an IgGk monoclonal antibody that can be detected as an individual monoclonal band on SPEP and serum immunofixation electrophoresis (IFE). It can be confused with the endogenous IgG-k M-protein of the patient during IFE interpretation. Co-migration can introduce a bias in M-protein quantification and can also mask clearance of the patient's M-protein by IFE. For optimal M-spike monitoring, our laboratory specialist will be informed if a patient is receiving daratumumab.

10.2.1 Hematologic Response Criteria

CR: Negative serum and urine immunofixation electrophoresis, normal serum free light chain ratio

VGPR: Reduction in the dFLC to <40 mg/L, dFLC = difference in involved and uninvolved serum free light-chain levels

PR: dFLC reduction by >50%, dFLC = difference in involved and uninvolved serum free light-chain levels

SD: Meets neither criteria for CR, VGPR, PR or PD

PD: An increase in FLC of 50% to > 100mg/L. From CR, any detectable M protein or abnormal FLC ratio (light chain must double). From VGPR, PR or SD, an increase in the serum M-protein from the lowest level by > 50%, as long as the absolute magnitude of this increase is > 0.5 g/dL; or an increase in the urine M-protein from the lowest level by 50%, as long as the absolute magnitude of this increase is > 200 mg/day; or an increase in the serum or urine monoclonal free light chain by > 50% from the lowest level, as long as the absolute magnitude is > 10 mg/dL (100 mg/L).

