6.0 ELIGIBILITY CRITERIA

6.1 Eligibility Criteria

- Histological diagnosis of primary systemic (AL) amyloidosis:
 - a. At least one tissue demonstrating positive Congo Red staining with characteristic apple green birefringence AND/OR characteristic appearance of fibrils on electron microscopy **AND**
 - b. Evidence of a clonal plasma cell dyscrasia:
 - i. Monoclonal protein in the serum and/or urine by immunofixation electrophoresis **AND/OR**
 - ii. Abnormal serum free light chain assay **AND/OR**
 - iii. Clonal plasma cell population in the bone marrow demonstrated by immunohistochemistry, flow cytometry or in situ hybridization **AND**
 - c. Evidence of organ involvement other than carpal tunnel syndrome. Confirmation of tissue diagnosis at all sites of organ dysfunction is encouraged, but not required.
- Must have received at least one prior treatment regimen of proven efficacy in the treatment of AL amyloidosis. If prior treatment included ASCT, at least 6 months must have elapsed between ASCT and study drug.
- Must be ≥ 18 years of age.
- Must have a performance status of 0-2 by ECOG criteria (see Section 10.4)
- Must have adequate hepatic function as evidenced by serum bilirubin values < 2.0 mg/dL; ALT and/or AST $< 3 \times \text{ULN}$ (bilirubin < 3 mg/dL allowed if related to Gilbert's syndrome).
- Must have an absolute neutrophil count $\geq 1000/\text{mm}^3$, hemoglobin ≥ 7.5 g/dL, and platelet count $\geq 50 \times 10^9/\text{L}$

6.2 Exclusion Criteria:

- Renal Insufficiency (CrCL $< 20 \text{ mL/min}$), calculated by Cockcroft-Gault Equation
$$\text{CreatClear} = \text{Sex} * ((140 - \text{Age}) / (\text{SerumCreat})) * (\text{Weight} / 72)$$

*Equation parameters such as **Sex** have two or more discrete values that may be used in the calculation. The numbers in the parentheses, e.g. (1), represent the values that will be used.*

The default unit of measure for weight is kilograms. Please verify that the correct unit of measure has been selected.

<http://reference.medscape.com/calculator/creatinine-clearance-cockcroft-gault>
- Mayo clinic cardiac biomarker stage IIIb (see appendix 14.3)
- Evidence of significant cardiovascular conditions as specified below:
 - NT-ProBNP > 8500 ng/L (Mayo Stage IIIb patients are excluded)

- New York Heart Association (NYHA) classification IIIB or IV heart failure (see Section 10.5)

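### A patient admitted on a marrow clone alone can already meet the written definition of complete response at screening and be counted as a responder without any change

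*Combined protocol and SAP*

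**What the plan says.** **Entry.** Section 6.1.b gives three kinds of evidence for a clonal plasma cell dyscrasia: "Monoclonal protein in the serum and/or urine by immunofixation electrophoresis", "Abnormal serum free light chain assay", and "Clonal plasma cell population in the bone marrow demonstrated by immunohistochemistry, flow cytometry or in situ hybridization". They are joined by AND/OR, so any one is enough. Section 10.0 adds that "Patients will not be required to have a delta FLC of 40 mg/L for study entry", and no minimum M-protein is written anywhere.

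**Response.** Section 10.2.1 defines the top category as "CR: Negative serum and urine immunofixation electrophoresis, normal serum free light chain ratio". The categories below it are worded as changes: VGPR is a reduction of dFLC to under 40 mg/L, and the PR entry begins "PR: dFLC reduction by >50" (percent). Section 10.0 also states: "Hematologic responses will be assessed by other hematologic measures of disease including M-spike and presence of clonal plasma cells in the bone marrow".

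**Marrow schedule.** The calendar in Section 9.0 marks the bone marrow biopsy in the screening column only. Its footnote, "Bone marrow biopsy and aspiration must have been repeated following any previous therapy > 1 cycle", concerns that screening sample.

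**Who is counted.** Section 11.1 plans 25 enrolled to obtain 20 evaluable for response, without defining *evaluable*. Section 11.3 (Statistical Methods) assigns the efficacy analyses to the safety population, meaning everyone who received at least one dose.

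**The concern.** An allowed entry state coincides with the best response category. For a patient whose disease shows only in the marrow, every element of CR is present at screening, and the one measure that shows the disease is not scheduled again. Scored by the written rule, that patient counts as a complete responder whether or not the drug has done anything.

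Hematologic response rate is the first secondary objective. It is estimated in one arm of 20 to 25 patients with no control group, so a response that needs no change goes straight into the estimate. No planned analysis separates such a patient from one whose markers converted on treatment.

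**Working it through.** The plan gives no expected response rate, power or error rate, so there is no stated figure to reproduce. The check is mainly a comparison of texts, followed by short arithmetic for scale.

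**Step 1. Compare the entry state with the CR definition.** Take a patient admitted on the marrow route alone.

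| Element of CR (10.2.1) | Must it be abnormal at entry (6.1.b)? | Possible screening value |
|---|---|---|
| Serum immunofixation negative | No | Negative |
| Urine immunofixation negative | No | Negative |
| Free light chain ratio normal | No | Normal |
| Change from baseline | Not part of CR | – |
| Marrow clearance | Not part of CR | – |

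All three required elements can be met before dosing. An unchanged patient meets them again at each three-monthly assessment.

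**Step 2. Look for a rule elsewhere that prevents this.**
- The marrow sentence in 10.0 has no threshold, feeds no category in 10.2.1, and has no post-baseline sample in 9.0.
- Calendar footnote 8 asks for a fuller panel once light chains normalize. The panel is not defined, and nothing says it includes marrow.
- *Evaluable* in 11.1 could have excluded such patients, but it is undefined, and 11.3 uses all dosed patients for efficacy.
- Section 10.2.2 shows that the plan does gate responses on baseline elsewhere: NT-proBNP response requires a baseline above 650 ng/L, and NYHA response requires baseline class 3 or 4. Hematologic CR has no such gate.

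**Step 3. Size per patient.** Let k be the number of such patients, n the denominator and p the true CR rate in everyone else. The observed CR rate is (k + (n − k)p)/n.

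With p = 0 this is k/n:
- n = 20: 1/20 = 5%, 2/20 = 10%, 3/20 = 15%.
- n = 25: 1/25 = 4%, 2/25 = 8%, 3/25 = 12%.

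The same 4 or 5 points per patient go into the overall hematologic response rate, taking that rate to include CR.

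Against a rate computed without these patients, the excess is k(1 − p)/n, which is smaller when p is larger. With k = 1 and n = 20, at assumed values of p:
- p = 10%: (1 + 19 × 0.10)/20 = 14.5%, an excess of 4.5 points.
- p = 40%: (1 + 19 × 0.40)/20 = 43%, an excess of 3 points.

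**Step 4. How likely is at least one?** The share s of such entrants is not in the documents. For assumed values, the probability is 1 − (1 − s)^n.

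| Assumed s | n = 20 | n = 25 |
|---|---|---|
| 0% | 0% | 0% |
| 2% | 33% | 40% |
| 5% | 64% | 72% |
| 10% | 88% | 93% |

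These figures show only how the answer depends on s; nothing in the documents favours one row.

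**The case against.** **6.1.b is a diagnostic criterion.** It sits under the histological diagnosis and does not describe disease on the day of screening. The Background speaks of patients in need of second-line therapy, and nothing suggests that marrow-only entrants were expected. This bears on frequency. It does not close the gap, because a diagnostic criterion leaves the screening values even less constrained.

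**The literal reading looks unintended.** Section 7.4.3 lists complete hematologic response among the reasons for leaving treatment, with continuation at the investigator's discretion. A patient in CR at screening would meet that item before dosing, which suggests a wording gap. That is fair, but the written rule still determines the count.

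**Such patients might be inferred to be certain false responders.** The documents do not support that. Section 10.2 warns that daratumumab can appear as a monoclonal band on serum immunofixation, and the calendar schedules the drug-specific assay for kappa disease only. If the band is attributed to the patient's clone, CR is not met.

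**It might also be inferred that nothing in the plan would reveal the problem.** That is too strong. Immunofixation and free light chains are collected at screening, so a listing of baseline values beside response would show it. What is missing is a rule or planned analysis that uses them.

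**The stakes are limited.** Hematologic response is secondary, all summaries are descriptive, no hypothesis is tested, and the interim rule in 11.2 concerns safety only. All of this stands.

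**Conclusion.** The point holds as a defect in the endpoint definition. As written, 6.1.b and 10.2.1 together allow a patient to be scored as a complete responder with no change, and neither 9.0, 10.0, 11.1 nor 11.3 prevents it. Each such patient adds 4 points (n = 25) or 5 points (n = 20) to the CR rate, compared with scoring that patient a non-responder.

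This rests on two assumptions: that at least one patient enters with negative immunofixation and a normal ratio, and that any drug band is not read as the patient's clone. The first cannot be judged from the documents, and the number may be zero. A reader might go further and conclude that the reported CR rate will be materially inflated; the documents do not support that, because they give no share of such entrants. The primary safety endpoint is unaffected. The amendment is still worth making, because a stated rule gives a wrong result and the data needed to correct it are already collected.

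**What to change.** 1. In 10.2.1 and 11.3 (Statistical Methods), define a hematologic-response-evaluable set: patients with a positive serum or urine immunofixation, or an abnormal free light chain ratio, at baseline. Section 11.3 must be amended too, because it now assigns efficacy to all dosed patients. Use the same definition for *evaluable* in 11.1.
2. Score CR only in that set. List the remaining patients separately as having no measurable blood or urine disease, and keep them in every safety analysis.
3. Reconcile the marrow clause in 10.0 with 10.2.1 and the calendar. Either remove it as a response measure, or give it a criterion and an assessment time. The choice is the investigators'.

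**Cost.** A few sentences in 10.0, 10.2.1, 11.1 and 11.3. Steps 1 and 2 need no new data. The response denominator may shrink by a patient or two, and the CR rate may look slightly less favourable. The planned allowance of 25 − 20 = 5 patients can absorb that if other losses are no more than three or four. Keeping marrow as a response measure under step 3 would add a post-baseline assessment.

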11.0 STATISTICAL CONSIDERATIONS

11.1 Sample Size Estimation

Estimated patient accrual and trial duration: The study will be designed as a single armed phase II trial, in which the response in 20 evaluable patients will be determined, with 25 patients enrolled to ensure that 20 are evaluable

Completion of accrual will be expected in ~2 years, with an additional year of monitoring and follow up after the last patient is enrolled.

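### For patients who enter with dFLC below 40 mg/L, the VGPR and PR wording in 10.2.1 permits different response counts from the same data

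*Combined protocol and SAP*

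**What the plan says.** Section 10.0 sets no dFLC minimum for entry: "Patients will not be required to have a delta FLC of 40 mg/L for study entry". It continues: "Hematologic responses will be assessed by other hematologic measures of disease including M-spike and presence of clonal plasma cells in the bone marrow". That second sentence is not expressly limited to patients with a low dFLC. Section 6.1 is consistent with their entry. An abnormal free light chain assay is only one of three and/or routes to showing a clone; another is "Clonal plasma cell population in the bone marrow demonstrated by immunohistochemistry, flow cytometry or in situ hybridization".

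Section 10.2.1 then gives the categories. CR rests on immunofixation and the free light chain ratio. VGPR is "VGPR: Reduction in the dFLC to <40 mg/L, dFLC = difference in involved and uninvolved serum free light-chain levels", and PR is "PR: dFLC reduction by >50" per cent. Neither has a baseline floor, and neither has an M-spike or marrow alternative. Amounts of M-protein appear only under PD. The rest fall into "SD: Meets neither criteria for CR, VGPR, PR or PD".

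In the Study Calendar (9.0), the marrow biopsy row is marked at Screening only. Its footnote ("Bone marrow biopsy and aspiration must have been repeated following any previous therapy") concerns marrow after earlier treatment, not follow-up on study. SPEP is scheduled every three months, but no M-spike response threshold is given.

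Section 11.1 plans for the response in 20 evaluable patients, "with 25 patients enrolled to ensure that 20 are evaluable", without defining evaluable. Section 11.3 (Statistical Methods) uses all treated patients for efficacy, applies no hypothesis test, and lists hematologic response rate as a secondary endpoint.

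**The concern.** A patient who starts below 40 mg/L already satisfies the numerical target for VGPR. The only thing left to satisfy is the word for a fall, and the plan does not say how large that fall must be or where it must start. Section 10.0 seems to anticipate the difficulty by pointing to other measures, but 10.2.1 does not carry those measures into VGPR or PR.

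The organ criteria in 10.2.2 show that the plan can set a floor when it wants one: the NT-proBNP response is confined to patients with a baseline above 650 ng/L. VGPR has no counterpart.

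At stake is the first secondary objective. Two analysts, each following the text in good faith, could report different hematologic response rates from one dataset. On the literal reading, a change of one or two mg/L would be counted as a very good partial response.

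**Working it through.** The plan states no target response rate, precision, alpha or power for this endpoint, so there is no figure of its own to reproduce. The check applies the 10.2.1 wording to example values and then bounds the effect.

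**Step 1. Three readings of the VGPR wording.** A: any fall that ends below 40 mg/L. B: the value must cross 40 from above. C: VGPR sits above PR in a ranked list and so presupposes the PR fall of more than 50%. The text chooses none of them. Example patients below 40 mg/L at baseline, assuming neither CR nor PD:

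| Baseline to follow-up (mg/L) | Change | A | B | C |
|---|---|---|---|---|
| 35 to 34 | 1/35 = 2.9% fall | VGPR | SD | SD |
| 20 to 19 | 1/20 = 5.0% fall | VGPR | SD | SD |
| 35 to 20 | 15/35 = 42.9% fall | VGPR | SD | SD |
| 35 to 15 | 20/35 = 57.1% fall | VGPR | PR | VGPR |
| 35 to 36 | 1/35 = 2.9% rise | SD | SD | SD |

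Two things follow. Under A, PR can never be the best category for these patients, because every fall is already VGPR. And responder status differs between readings only for non-CR patients whose dFLC falls by more than 0 and up to 50%. With a larger fall the label may change, but the patient is a responder under all three.

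**Step 2. Bound on the response rate.** Let k be the number of patients below 40 mg/L at baseline and N the number analyzed. The documents do not give k.

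- Ceiling: k/N. It is reached only if every one of the k patients has a fall in the affected range.
- Tighter limit: suppose 29% of the k patients have CR or a fall above 50%. They count under every reading, so the gap is at most (1 − 0.29)k/N = 0.71k/N. The 29% is the myeloma response rate in section 2.0, the only daratumumab response rate in the documents. Using it here is an assumption.

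| k (assumed) | k/N, N=20 | 0.71k/N, N=20 | k/N, N=25 | 0.71k/N, N=25 |
|---|---|---|---|---|
| 0 | 0 | 0 | 0 | 0 |
| 2 | 10% | 7.1% | 8% | 5.7% |
| 4 | 20% | 14.2% | 16% | 11.4% |
| 6 | 30% | 21.3% | 24% | 17.0% |

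N=20 is the evaluable number in 11.1. N=25 applies if all enrolled patients are treated and 11.3 is followed.

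**Step 3. What a floor at 40 mg/L does.** The first four rows of the Step 1 table are no longer scored on dFLC. Cases such as 100 to 35 and 60 to 39 mg/L remain VGPR.

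**Step 4. Precision after the floor.** With k=4 and about 29% responding, the expected counts are 0.29 × 16 = 4.6 and 0.29 × 20 = 5.8, rounded to 5/16 and 6/20. The exact (Clopper-Pearson) 95% intervals are 11% to 59% for 5/16 = 31%, and 12% to 54% for 6/20 = 30%.

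**The case against.** The strongest reply is that little is at risk. The endpoint is secondary and descriptive, k may be zero, and even the ceiling of 20 points for k=4 is narrower than the exact interval of 12% to 54% for 6/20. All of that stands and keeps the point minor. It does not answer it: sampling error cannot be avoided at this size, whereas a difference between readers of the same rule can be removed by wording.

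A second reply is that 10.0 does not promise separate criteria for low-dFLC patients. This also stands. The sentence on other measures is not tied to them and does not say that it replaces dFLC, and CR already uses serum and urine immunofixation. But read more widely, the sentence fits 10.2.1 no better, since VGPR and PR contain no M-spike or marrow measure for anyone.

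A third is that a trained reader would never score 35 to 34 mg/L as VGPR. Probably so, but that reader would be using reading B or C, which the text does not state.

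A reader might also infer that hematologic response cannot be scored at all in these patients. The documents do not support that. CR and PD are defined without the VGPR wording, SD remains as the residual category (though its count moves with VGPR), and a fall above 50% can still be calculated.

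**Conclusion.** The point holds as a minor defect of definition. For patients entering below 40 mg/L, 10.2.1 does not settle whether a small fall is VGPR or SD, and 10.0 points to measures that VGPR and PR do not contain. The reported response rate can differ by at most k/N. It differs by at most 0.71k/N if 29% of these patients have CR or a fall above 50%: 14 points for k=4 and N=20. Both k and the 29% are assumptions, and the effect is zero if no such patient is enrolled, or if the undefined term evaluable already excludes them.

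Two stronger conclusions are tempting and should not be drawn. One is that the response rate will be inflated by 20 points; that figure is a ceiling for an assumed k, not an estimate. The other is that the trial's main conclusions or its size are undermined. The primary endpoint is infusion safety, and 11.1 contains no power or precision calculation that depends on this rule.

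No claim is made about small falls from just above 40 mg/L, such as 41 to 39 mg/L (2/41 = 4.9%). Reading C would also reclassify some patients who start above 40, such as 60 to 39 mg/L (35.0%). That is a separate question.

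**What to change.** - **10.2.1:** limit dFLC-based VGPR and PR to patients with a baseline dFLC of at least 40 mg/L, the threshold that 10.0 already names. PR needs the floor as well as VGPR; otherwise 35 to 15 mg/L would still score as PR. Report patients below 40 mg/L separately, with CR as their scorable response.
- **11.3 (Statistical Methods):** name the dFLC-measurable subset of the treated population as the denominator for dFLC response. Without this, the new 10.2.1 would conflict with the use of all treated patients for efficacy.
- **11.1:** state whether the 20 evaluable patients means this subset. Do not enroll more for this purpose; if fewer than 20 are measurable, restate the figure.
- **10.0 and the calendar:** reconcile the M-spike and marrow sentence with 10.2.1. Either give each measure a response threshold and scheduled follow-up, or remove it. An M-spike rule would also have to deal with the daratumumab interference described in 10.2.

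The cost is wording in four places and one extra split in the response table. The statistical price is a smaller denominator and a wider interval, such as 11% to 59% for 5/16 against 12% to 54% for 6/20. The rate itself may move either way; in that example it goes from 30% to 31%.
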